8.7 Patient Transfer and Withdrawal

8.7.1 Patient Transfers

It is very unlikely that participants taking part in BESS will be transferred during their trial treatment, given the severity of illness of participants and the short time period for administration of the intervention. In the unlikely scenario that a BESS participant is transferred while they remain intubated, their trial treatment will end at transfer unless they are transferred directly to another BESS site. For participants transferred to another participating trial site the receiving trial site must take over responsibility for the participant.

A copy of the participant CRFs should be provided to the new site. The parent will have to sign a new consent form at the new site, and until this occurs, the participant remains the responsibility of the original site.

If a participant is transferred to a site that is not taking part in BESS then they will be withdrawn from the trial and will receive no further interventions. Their care will revert to the standard practice and will not be affected by the withdrawal from the trial. The CTRC should be notified in writing of all participant transfers, whether or not to a participating trial site.

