#### 17. Efficacy Evaluations

#### 17.1. Data Sets Analysed

The principle of intention-to-treat, as far as practically possible, will be the main strategy of the analysis adopted for the primary outcome and all secondary outcomes. These analyses will be conducted on all randomised participants, in the group to which they were randomised, and for whom the outcome(s) of interest have been observed/measured. No imputations will be made.

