# 17.4.1.1. Derivation

The duration of mechanical extubation will be calculated by identifying the date and time (OAODATXD) associated with final extubation as indicated by OAOOUTCC = "Successful" on the Observations and Outcomes CRF. The difference between the date/time of randomisation taken from the Almac randomisation log and the date/time of successful extubation will be calculated in hours and transformed using natural logarithms.

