# 17.4.1.2. Analysis

Descriptive statistics will be presented split by treatment and overall for the time from randomisation to final successful extubation (before the data is transformed) and time off MV due to failed extubation. The summaries will be presented as median and interquartile range as the data is likely to be skewed.

A comparison of group means will be conducted using a two-sample t-test on the log transformed data (the log transformation will be done using natural logarithms). The between group difference of the log transformed data will then be back transformed by taking the exponent to give the geometric mean difference and the corresponding 95% confidence interval.

A linear mixed effects model will also be fitted on the log transformed data, using ANCOVA to test for a difference between groups with adjustment for the stratification factor of time on ventilation prior to randomisation (<24h and  $\geq$ 24h), sex and adjusted age at enrolment as a fixed effects and site as a random effect (random intercept only). The exponentiated between-group difference and corresponding 95% confidence interval will be reported.

The approach to the primary outcome analysis will be a compete case analysis and will only include those participants for which the primary endpoint has been observed. If there are any participants who have not recorded a successful extubation at the point at which they were last followed up (e.g. consent for follow up has been withdrawn) then sensitivity analysis will be conducted including these participants to assess the robustness of the primary outcome analysis.

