#### 17.4.2.1. Derivation

The time to readiness for SBT will be calculated by identifying the date and time (OAODATCD) associated with the observation for which readiness for SBT is first reported as indicated by OAOPSBTC = "Yes" **and** the senior clinician is in agreement with the readiness for SBT as in indicated by the variable OAOCLSTC = "Yes" on the Observations and Outcomes CRF. That is, if the SBT criteria is met numerically (as described in section 8.1.4.1 of the protocol) but the senior clinician is not of the opinion that the infant is ready for an SBT then the infant does not meet the definition of readiness for SBT.

The difference (in hours) between the date/time of randomisation taken from the Almac randomisation log and the date/time of the observation at which readiness for SBT is first reported will be calculated and transformed using natural logarithms.

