## 18. Missing data and withdrawals

Missing data will be quantified for all outcomes presented in the final analysis report. Where known, reasons for missingness will be given.

Withdrawals from trial will be summarised and presented as line listings detailing:

- 1. Site
- 2. Time from randomisation to withdrawal
- 3. Decision to withdraw participant made by:
  - a. Clinician
  - b. Parent/person with parental responsibility
  - c. Both clinician and parent/person with parental responsibility
- 4. Reason for withdrawal:
  - a. Death
  - b. Lost to follow-up
  - c. Transfer to non-participating site
  - d. Withdrawal of consent for follow-up
  - e. Other (specify)

Every effort will be made to collect follow-up data even in the event of participants discontinuing the trial intervention. In the case of withdrawals from study, available data will still be included using an intent-to-treat approach.

#### 19. Additional analyses Additional analysis 1

A sensitivity analysis of the primary analysis will be done to assess the robustness of the primary analysis. This will be done using a Cox proportional hazards model and will allow the censoring of patients who do not observe the primary endpoint of successful extubation. The start-point and end point for patients having the event of successful extubation will be the same as those defined in section 17.4.1.1. For patients who do not have a successful extubation recorded these will be censored at the last date and time (OAODATXD) an observation is recorded on the Observations and Outcomes CRF. The cox proportional hazards model will include the allocated treatment and time on ventilation prior to randomisation as covariates.

#### Additional analysis 2

A subgroup analysis of the primary outcome will be undertaken, This was based on a recommendation from the Trial Steering Committee who met on the 20th February 2024.

The subgroup analysis will examine the primary outcome stratified by whether the baby was born prematurely or not and will include an interaction term between treatment and prematurity in the linear mixed effect model described in 18.4.1.2.

Results will be presented from the model with the interaction result alongside.

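### Infants who die before successful extubation leave the primary analysis, and the one planned check has no rule for death

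*SAP*

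**What the plan says.** The primary endpoint is derived from the case report form as the time "associated with final extubation as indicated by OAOOUTCC" being recorded as successful (SAP 17.4.1.1). The analysis is complete-case and "will only include those participants for which the primary endpoint has been observed" (SAP 17.4.1.2). SAP 17.1 adds that "No imputations will be made".

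For infants without a recorded successful extubation, SAP 17.4.1.2 promises that "sensitivity analysis will be conducted including these participants to assess the robustness of the primary outcome analysis"; its example is withdrawal of consent. SAP 19, Additional analysis 1, gives the form, a Cox model: "For patients who do not have a successful extubation recorded these will be censored at the last date and time (OAODATXD" on the Observations and Outcomes form. Death is not mentioned there.

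The protocol commits to intention to treat for this outcome (8.4.1, 11.5). On transfers it says: "If a participant is transferred to a site that is not taking part in BESS then they will be withdrawn from the trial" (8.7.1). SAP 18 lists death and transfer to a non-participating site among the withdrawal reasons, so both are foreseen. For PICU and hospital stay, SAP 17.4.8.1 does state what happens when an infant dies. For the primary outcome no such rule is given.

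**The concern.** Death before extubation is not ordinary missing data: the endpoint can never exist for that infant. Leaving the infant out selects on a post-randomisation outcome. If such infants would have been ventilated for a long time, the arm with more of them loses part of its long tail and looks better on duration. The bias can favour either arm. A treatment that raised mortality on the ventilator would be flattered, and one that lowered it would be understated.

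A sensitivity analysis should show whether this happened. Censoring deaths at the last observation asks how fast infants still alive and ventilated are extubated. That question is legitimate, but it is largely insensitive to how many infants died.

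**Working it through.** **Inputs.** Placebo mean 4.83 days, surfactant mean 4.08 days, SD 2.5 days in each, two-sided 5% level, 5% dropout (protocol 11.3). Mortality 1.75% (protocol 3.2) and 1-2% (protocol 10.2.3).

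**The plan's own figure.** The log variances are ln(1 + (2.5/4.83)²) = 0.2374 and ln(1 + (2.5/4.08)²) = 0.3188. The log difference is ln(4.08/4.83) − (0.3188 − 0.2374)/2 = −0.2095, a geometric mean ratio of 0.811. Then n = (0.2374 + 0.3188)(1.960 + z)²/0.2095² gives 99.5 (100 per group) at 80% power and 133.2 (134) at 90%. 134/0.95 = 141.05, so 142 per group and 284 in total. All of this matches the protocol.

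**Expected deaths.** 284 × 1% = 2.8; × 1.75% = 5.0; × 2% = 5.7. The chance of at least one death is 1 − 0.99^284 = 94% at the lowest rate. These are all deaths; only those before successful extubation matter here.

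**Power.** Losing five infants leaves 139.5 per arm on average and about 91% power. Sample size is not the problem.

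**Bias.** I simulated 3,000 trials per scenario with 142 infants per arm and log-normal durations from the planning inputs. Assumptions: deaths fall at random within the longest-ventilated quarter of an arm, death comes at 20-100% of the would-be ventilation time, and there is no other loss. A hazard ratio (HR) for extubation above 1 favours surfactant.

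| True effect on duration | Deaths, placebo/surfactant | Complete-case ratio | Significant for surfactant | Cox HR, deaths censored | HR, dead infants kept in risk set |
|---|---|---|---|---|---|
| None | 0/0 | 1.001 | 2.9% | 0.996 | 0.996 |
| None | 3/2 | 1.006 | 1.7% | 0.995 | 1.018 |
| None | 0/5 | 0.978 | 6.2% | 1.012 | 0.903 |
| None | 0/8 | 0.964 | 9.8% | 1.022 | 0.866 |
| Planned | 0/0 | 0.811 | 92.1% | 1.320 | 1.320 |
| Planned | 0/5 | 0.791 | 95.5% | 1.339 | 1.170 |
| Planned | 5/0 | 0.828 | 85.1% | 1.315 | 1.448 |
| Planned | 0/8 | 0.776 | 97.7% | 1.359 | 1.117 |

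Near-balanced deaths hardly matter. Five to eight deaths in one arm move the complete-case ratio by 2-4% (for example 0.791/0.811 = 0.975 and 0.776/0.811 = 0.957). The censoring Cox HR barely moves (1.32 to 1.34-1.36), whereas keeping dead infants in the risk set moves it to 1.17 or 1.12. If treatment does not affect mortality, five deaths all fall on surfactant with probability 1/32.

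**Price of a death-inclusive check.** Under the planned effect, a worst-rank Wilcoxon test (unstratified here) had power of 90.5% with no deaths and 86.7% with deaths 0/5.

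**Censoring variable.** SAP 17.4.1.1 finds the endpoint by "identifying the date and time (OAODATXD) associated with final extubation". SAP 19 uses the same variable as the time of the last recorded observation. SAP 17.4.2.1 uses another variable for observation time: "the date and time (OAODATCD) associated with the observation for which readiness for SBT is first reported".

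**The case against.** Several points on the other side stand.

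- Deaths after successful extubation stay in the analysis. The group still ventilated at the end should be almost empty, because data are collected to hospital discharge and analysis waits for complete follow-up.
- Protocol 8.7.1 calls transfer while intubated very unlikely. Protocol 8.8 requires contact attempts after loss through transfer, SAP 18 promises every effort to obtain follow-up, and extubation is recorded in PICANet (protocol 8.4.1), whose data are collected to day 90. The protocol reviewed is version 2.0, while the SAP cites versions 3.0 and 6.0, so 8.7.1 may since have changed.
- SAP 17.1 qualifies intention to treat as far as practicable, and exclusions are to be reported with reasons.
- Deaths are compared by arm (SAP 17.5.5, 17.5.6), so an excess would be visible. That comparison is weak, however. For five deaths against none with 142 per arm, the two-sided Fisher p-value is 2 × (142·141·140·139·138)/(284·283·282·281·280) = 0.06, and the result is not combined with duration.

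A reader might infer that the Cox analysis is invalid because it treats dead infants as if they would later be extubated at the usual rate. The documents do not support that. The SAP makes no such statement, the cause-specific hazard ratio is valid, and the assumption matters only if the result is read as a probability of extubation. Censoring is also the ordinary treatment for live infants whose data end.

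**Conclusion.** The point holds as a gap in how the primary outcome handles death. Infants who die before successful extubation are excluded, and the only planned check would not reveal bias from unequal deaths. The expected size is small: negligible with balanced deaths, and about 2-4% on the geometric mean ratio if 5 to 8 deaths fall in one arm. That range rests on the assumption that those infants are among the longest-ventilated. The planned sample size and primary test need not change.

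Two stronger readings are not supported. One takes the whole 5% dropout allowance as the longest-ventilated infants of a single arm. With the placebo log SD of √0.2374 = 0.487, that truncation shifts the log mean by 0.487 × 0.1031/0.95 = 0.053, or 25% of the planned log effect. But the 5% is general dropout, and the documents imply about 3 to 6 deaths over both arms. The other reading is that never-extubated infants have no censoring time. Whether OAODATXD is blank for them depends on a form that is not in the documents, so only a reconciliation is warranted.

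**What to change.** 1. **SAP 17.4.1.2 and 19.** Keep the primary analysis. Pre-specify beside it an all-randomised sensitivity analysis in which death before final extubation counts as the worst outcome, for example a worst-rank stratified Wilcoxon test. As an alternative or addition, treat death as a competing event in the time-to-extubation analysis by keeping dead infants in the risk set to day 90. Keep ordinary censoring for live infants whose data end, and state how they enter the rank analysis.
2. **Protocol 8.7.1, 8.8 and SAP 18.** Reconcile these so that transfer to a non-BESS unit ends trial intervention, as 8.7.1 already says, but not data collection. Obtain the extubation time from the receiving unit or PICANet where consent allows.
3. **SAP 17.4.1.1 and 19.** Reconcile the two uses of OAODATXD, and confirm that the censoring variable is populated for infants never extubated.

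The cost is SAP wording, a short protocol clarification, a little programming and queries for very few infants, with no extra patients. The changes should be made before treatment codes reach the statistical team; any made later should be labelled post hoc.

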#### 17.4.2. Secondary Outcome 1: Readiness for SBT

This outcome will assess if there is any evidence of a difference in the length of time from randomisation to participant meeting the criteria for readiness for SBT between arms.

#### 17.4.2.1. Derivation

The time to readiness for SBT will be calculated by identifying the date and time (OAODATCD) associated with the observation for which readiness for SBT is first reported as indicated by OAOPSBTC = "Yes" **and** the senior clinician is in agreement with the readiness for SBT as in indicated by the variable OAOCLSTC = "Yes" on the Observations and Outcomes CRF. That is, if the SBT criteria is met numerically (as described in section 8.1.4.1 of the protocol) but the senior clinician is not of the opinion that the infant is ready for an SBT then the infant does not meet the definition of readiness for SBT.

The difference (in hours) between the date/time of randomisation taken from the Almac randomisation log and the date/time of the observation at which readiness for SBT is first reported will be calculated and transformed using natural logarithms.

# 17.4.2.2. Analysis

Descriptive statistics will be presented split by treatment and overall for the time from randomisation to readiness for SBT (before being transformed). The summaries will be presented as median and interquartile range as the data is likely to be skewed.

The frequency and percentage of the number of times each participant is recorded as meeting the criteria for readiness for SBT will presented split by treatment and overall.

The comparative analysis will be as described in 17.4.1.2 but will just involve the two-sample t-test, a linear mixed effects model will not be used for this outcome.

A sensitivity analysis will be conducted using the first time a patient meets the numerical criteria for SBT. The sensitivity analysis will be as described in 17.4.1.2 but will just involve the two-sample t-test, a linear mixed effects model will not be used for this outcome.

# 17.4.3. Secondary Outcome 2: Number of trial interventions

This outcome will assess if there is evidence of a difference in the number of trial interventions (both poractant and placebo) given to the infants between trial arms.

# 17.4.3.1. Derivation

A successful delivery of the intervention is indicated on the Treatment CRF where the MACRO variable TRTINSTC = "Intervention completed". An infant can receive up to three doses of intervention.

#### 17.4.3.2. Analysis

A two-way table will be presented with the frequency of interventions received vs allocated treatment. A Chi-squared test for trend will be used to test for an association between allocation and the number of trial interventions if the expected cell frequencies are greater than five and Fisher's exact test will be used if they are not. The Chi-squared test statistic and corresponding p-value will be presented for the test.

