8 PARTICIPANT TIME LINE, ASSESSMENTS AND PROCEDURES

8.1 Administration of Intervention

The first trial intervention must be administered within 2 hours of randomisation with subsequent doses (if required) at 12 and 24 hours post randomisation. A grace period of one hour either side of the anticipated administration time is permitted.

- Randomisation; T0
- First intervention must be given within two hours; between T0 and T2
- Second intervention should be given 12 hours after randomisation; at T12 (+/- 1 hour)
- Third intervention should be given 24 hours after randomisation; at T24 (+/- 1 hour)

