#### 17.5.1.2. Analysis

The total number of occurrences of failure to administer intervention due to adverse event will be presented overall and for both treatment groups and also the number of patients in each group will be reported.

A two-way table of the frequency failed intervention delivery per infants by allocated treatment group will be presented. The comparative analysis between arms will be as described in section 17.4.3.2.

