#### 17.5.2.2. Analysis

A two-way table of the frequency of events of air leak per infants by allocated treatment group will be presented. The comparative analysis between arms will be as described in section 17.4.3.2.

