#### 17.5.3.1. Derivation

The outcome is captured on JotForm Form 1 90-day Readmission and the frequency is captured in the column: "How many times was your child admitted to hospital in the 3 months after they took part in BESS?" and can take values from zero to six or more.

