#### 17.5.3.2. Analysis

A two-way table of the frequency of parent reported readmission to hospital by allocated treatment group will be presented. The comparative analysis between arms will be as described in section 17.4.3.2.

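### SAP 17.4.3.2 replaces a trend test with an unordered Fisher's exact test when cells are sparse; for parent-reported readmission this is near certain and costs power

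*SAP*

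**What the plan says.** SAP 17.4.3.2, on the number of trial interventions, sets the main test: "A Chi-squared test for trend will be used to test for an association between allocation and the number of trial interventions". The same sentence makes this conditional: "if the expected cell frequencies are greater than five and Fisher's exact test will be used if they are not". The outcome is an ordered count: "An infant can receive up to three doses of intervention".

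Three safety outcomes refer back to this rule:

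- **Failed administration** (17.5.1.2): "A two-way table of the frequency failed intervention delivery per infants by allocated treatment group will be presented".
- **Air leak** (17.5.2.2): "A two-way table of the frequency of events of air leak per infants by allocated treatment group will be presented".
- **Readmission** (17.5.3): the count "can take values from zero to six or more", and "The comparative analysis between arms will be as described in section 17.4.3.2".

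The SAP names no exact or ordered test for the sparse case, does not plan to merge categories, and gives no expected rates for these outcomes. The separate rule in 17.4.6.2, also chi-squared with a Fisher fallback, serves 2-by-2 outcomes and adds a relative risk.

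**The concern.** A trend test asks whether counts tend to be larger in one arm than in the other. Fisher's test extended to a 2-by-k table gives the same p-value if the columns are shuffled, so it asks only whether the two distributions differ in any way. Under 17.4.3.2 the choice between these questions is made by how thin the rarest category is, not by the purpose of the outcome.

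Readmission is the most exposed outcome. It has up to seven categories with a probably thin upper tail, and 17.5.3.2 plans a table and this test but no effect estimate. If readmissions shift consistently between arms, the planned p-value is less likely to show it than the trend test that the SAP names first.

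**Working it through.** **Inputs from the documents.** Protocol 11.3: mean 4.83 against 4.08 days, SD 2.5, two-sided 0.05, 5% dropout. Protocol 7.3: 1:1 allocation, within 48 hours of intubation. SAP 17.4.3.1: 0 to 3 doses. SAP 17.5.3.1: readmissions 0 to 6 or more. I read the rule as requiring every expected cell to exceed five, which is its natural meaning although the SAP does not say so.

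**The plan's own sample size.** The log variances are ln(1 + 0.518²) = 0.237 and ln(1 + 0.613²) = 0.319. The difference in log geometric means is ln(4.08/4.83) − 0.5 × (0.319 − 0.237) = −0.209.

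- 80% power: (1.960 + 0.842)² × 0.556 / 0.209² = 99.5, so 100 per group.
- 90% power: 133.2, so 134 per group.
- Dropout: 134/0.95 = 141.05, so 142 per group and 284 in total.

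This reproduces the protocol.

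**Threshold for the switch.** Expected cell = column total × 142/284 = half the column total. It exceeds five only if the column total is at least 11, which is 11/284 = 3.9% of infants. This must hold for every category that occurs.

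**How often the switch happens (simulated, 142 per arm).**

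| Outcome | Fallback used |
|---|---|
| Readmission, all scenarios | 89-100%, nearly always with three or more categories |
| Failed administration | 51-94% |
| Air leak, some infants with two | 97-99% |
| Air leak, only 0 or 1, at 3% against 10% | 2% |
| Doses | 0-99.9% |

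Doses are given "with subsequent doses (if required) at 12 and 24 hours post randomisation". The dose distributions use the protocol's own log-normal ventilation times, less an assumed delay from intubation to randomisation. With no infant at zero doses, the fallback rate is 95%, 59%, 1% and 0% at delays of 12, 24, 36 and 48 hours. With 1-2% of infants at zero doses it is 93-99.9% at every delay.

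**Power: rule as written against an exact trend test, both at two-sided 0.05.**

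| Outcome (assumed rates) | SAP rule | Exact trend |
|---|---|---|
| Readmission: placebo mean 0.2-0.8, rate ratio 0.5-0.7, Poisson or overdispersed | 45-65% | 54-80% (gain 3 to 29 points) |
| Air leak as 0/1/2, two scenarios | 53%, 31% | 54%, 30% |
| Failed administration: 1-3% against 4-8% per dose | 78, 84, 85% | 76, 83, 87% |
| Doses, delay 12-24 h, none at zero | 48-72% | 51-75% |
| Doses, delay 12-24 h, 1-2% at zero in both arms | 45-66% | 17-56% |

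In the last row the simulated difference is not monotone: the zero-dose share is equal in both arms while the other categories shift. Where only two categories occur the table is 2-by-2, no order is lost, and the two exact tests had identical power.

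**One illustrative readmission table (assumed).** Counts at 0/1/2/3/4 readmissions are 112/21/6/2/1 in one arm and 97/26/10/6/3 in the other. Column totals are 209/47/16/8/4, so expected cells are 104.5/23.5/8/4/2 and the rule selects Fisher's test. Full enumeration gives p = 0.25. The arms have 43 and 76 readmissions, and the exact trend test on the same table gives p = 0.022.

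**The case against.** Several stronger readings are tempting, and the documents do not support them.

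- **That the trend test would hardly ever be run for any of the four outcomes.** For doses this turns on the zero-dose share and the time to randomisation, neither of which the documents give. For failed administration and air leak it turns on unknown event rates.
- **That all four outcomes lose power.** Only readmission shows a clear loss. Air leak and failed administration show none, and for doses the result can reverse.
- **That the SAP asks a directional question.** It asks about a difference or an association. The order enters only through the named trend test.
- **That an excess of readmissions would be hidden.** The full table by arm is presented whatever the p-value. Hospitalisation is also a seriousness criterion (Protocol 10.1), and serious events that sites learn of are reported (Protocol 10.7) and tabulated (SAP 20.2).

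It can also be said that these outcomes are secondary or safety outcomes for which the trial was not sized, and that the upper end of the readmission loss needs favourable assumptions. Both points are fair and limit the weight of the finding. They do not justify the rule. Nothing else in the SAP restores the ordering, and where Fisher's test did better for doses it was by detecting a non-monotone pattern that the SAP's named test does not target.

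**Conclusion.** The concern holds for readmission. The fallback is near certain, and the loss is roughly 3 to 29 points of power against a test that is also exact, so it is not caused by comparing an exact test with an approximate one. The size rests on assumed readmission means, rate ratios and dispersion, and on all 142 infants per arm contributing data. The sample size comes from the protocol supplied, while the SAP refers to later protocol versions.

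For number of doses, failed administration and air leak, the finding is only that the hypothesis tested should not change with sparsity; no general loss of power is claimed. The primary analysis of ventilation time does not use this rule.

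**What to change.** In SAP 17.4.3.2, replace the Fisher clause so that the sentence ends: *an exact Cochran-Armitage trend test, with the count as the score (6 or more scored as 6), will be used if they are not.* Sections 17.5.1.2, 17.5.2.2 and 17.5.3.2 then inherit it by their existing cross-references. Keep Fisher's exact test for the 2-by-2 outcomes in 17.4.6.2. Naming one test and its scores leaves the analyst no choice to make after seeing the data.

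The cost is one sentence and an option in the software already specified, with no new data. It should be made before the randomisation codes are released to the statistical team. The downside is slightly less sensitivity to non-monotone differences, which the trend test that the SAP names does not target either.
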